9.5.4 Quality of Life/Global Impression

For these scales and associated subscales, differences from baseline will be calculated and methods described for analysis of the primary outcome will be used to test for differences between treatment groups from baseline and 6 and 12 months.

9.5.5 Safety and Initiation of Additional Treatment

We will describe rates of sling revision due to worsening OAB symptoms and rates of additional treatment.

9.5.6 Determine MIDs and Clinically-Meaningful MUI Definitions

We will explore potential MIDs for UDI total score and stress and irritative subscores for this MUI population. MIDs will be calculated using anchor- and distribution-based approaches. Potential anchors include global impression of change, incontinence episodes from the bladder diary, and request for additional treatment. The change from baseline UDI total score and stress and irritative subscores for each ESTEEM participant will be compared to the MIDs estimated from the ESTEEM data, and the percentage of participants who meet or exceed the MID will be compared between treatment groups..

We will attempt to create threshold definitions, based on baseline measures of the UDI, IIQ, OAB-q, UDE, and baseline bladder diary parameters in isolation and in combination, that are predictive of clinical success at 1 year. Definitions of success will be based on a change from baseline in total UDI score, UDI-irritative score or UDI-stress score at least as large as the MID for this MUI population.

9.5.7 Compare Pelvic Floor Muscle Strength

As mentioned above, all women will undergo PFM strength measurements using the Peritron device by masked coordinators at baseline, postoperative at 2 weeks, 8 weeks (end of intervention), and 12 months (primary endpoint). The difference in the maximum pelvic floor muscle contraction pressure (maximum amplitude) will be compared between the BPTx and the control groups. A table of comparative studies using the Peritron device to measure PFM strength changes with PFM therapy is provided in Table 12 of the protocol.

Based on the existing comparative studies using the Peritron, continent women have a maximum amplitude PFM contraction between 36-45 cm H₂O. Incontinent women have significantly lower maximum contractions, ranging from 15.5 to 26.5 cm H₂O, with most studies showing a maximum contraction of 25 cm H₂O. In these studies, incontinent women can improve their maximum contraction pressure up to 34-41 cm H₂O with PFM training, which is comparable to continent women. In addition, these studies report women experience significant improvement in UI symptoms, although there is limited information on the direct specific relationship between PFM strength changes and UI symptom changes.

Assuming that women in ESTEEM will have a mean baseline PFM maximum contraction amplitude of 25 cm H₂O, and that women randomized to control will not demonstrate significant improvement postoperatively (no change from mean maximum amplitude of 25 cm H₂O (SD 13), and that women randomized to BPTx will demonstrate improvement to 35 (SD 13) to 40 (SD 16) cm H₂O at 6-12 months, the power to detect a difference between the groups with the current ESTEEM sample size of 400 women would be greater than 0.99. Also, the difference from 25 (SD 13) that we could detect with 80% power is 3.66 cm H₂O between groups and with 90% power we could detect a difference as small as 4.23 cm H₂O.

For analyses, we will compare the mean change from baseline in PFM maximum contraction strength between the BPTx and control groups at 8 weeks and at 12 months. General linear mixed modeling will be used, controlling for stratification factors and time (8 weeks and 12 months). We will test whether there is significant interaction between treatment group and time. Because additional treatment is not expected to impact this outcome, it will be ignored for the purpose of this analysis. We will estimate the correlation between PFM strength and UI symptoms at baseline and at 12 months. Using regression models, we will also explore potential predictors of unsuccessful pelvic floor muscle strengthening and urge suppression and their effects on urinary outcomes. We will assess the effect of self-efficacy, adherence, and barriers to performing pelvic muscle contractions and behavioral therapy.

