3.2 Masking issues

It is not feasible to mask the patients or interventionists to the BPTx intervention due to the nature of the treatment being studied. The team considered “sham” visits with interventionists; however, based on expert interventionist opinion, sham interventions for UI involving the pelvic floor are extremely difficult to design in a way that is convincing yet maintains the integrity of the intervention itself. We also considered using “general massage” as a potential control group; however, there is some evidence suggesting that psychological stress is associated with OAB and irritative symptoms which could potentially contaminate the control group.⁴¹ Issues of adherence (or over-adherence) in the massage group are also possible, as women could schedule these independently from the study. For these reasons, the team decided it was not feasible to incorporate any sham procedures in the control group.

Study surgeons and outcome assessors will be masked to treatment assignment. All outcome measures will be collected by masked outcome assessors. Study coordinators / clinical staff performing objective measurement of PFM strength will be masked (Aim 7). All patient-reported outcomes (PROs) will be administered prior to other clinical assessments or procedures.

Table 2. Masking in ESTEEM

Study individual	Masking
Study participant	No
Interventionist	No
Outcome assessors (includes clinical staff performing PFM measurement)	Yes
Study surgeon	Yes

Efforts will be made by unmasked research assistant/staff members to remind the patient that the surgeon is masked to her treatment assignment. If she desires additional treatment, it is likely the surgeon would offer BPTx as additional treatment and she will be reminded that she can decline additional BPTx without revealing to her surgeon that she received the BPTx intervention. Such methods have been effective for past PFDN trials (e.g. OPTIMAL trial⁴²).

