The overarching goal of ESTEEM is to evaluate the effect of combined treatment on improving both SUI and UUI outcomes in women with MUI. Therefore, any request for additional treatment for any lower urinary tract symptoms (SUI, UUI/OAB, voiding dysfunction) before the 1 year outcome for either of these symptoms will be considered treatment failure. The team agreed it would be difficult to withhold additional treatment from either group for the 1 year study duration; however, any additional treatment should be initiated after the acute postoperative recovery period. Clinically, some women may experience immediate

exacerbation of OAB symptoms after MUS followed by improvement, whereas other women may experience initial improvement but then recurrence of OAB symptoms several months later. Therefore, the team came to a consensus that any additional treatment should be deferred until 3 months postoperatively when OAB symptoms would be expected to have reached a baseline. This will allow enough time for complete physical and tissue recovery from the surgical procedure, will allow for assessment of potential BPTx early benefits, and will provide information on the natural course of OAB symptoms in the early postoperative period which is important for clinical counseling and decision-making. Any subjects receiving additional treatment prior to the 3 month time point will be considered a protocol deviation.

In the event that a randomized participant decides not to undergo surgery but then later changes her mind and has MUS surgery, the surgery will be considered additional treatment. For purposes of calculating follow up windows, the date of the original planned surgery that did not occur will be Time 0.

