Subjects who initiate additional treatment will be asked to complete all primary and secondary outcome measures prior to initiation of additional treatment. The type of additional treatment will not be limited and will be left to the physician's clinical judgment. This may include (but is not limited to) behavioral and/or pelvic floor therapy, continence pessary, medical therapy, other procedure-based treatments (posterior tibial nerve stimulation, Botox), and surgical (sling revision, re-placement, sacral neuromodulation). Statistical models designed to specifically account for subjects who initiate additional treatment will be used. Please see Section 6, Statistical Considerations section for details on how the analysis of primary and secondary outcomes measured at 1 year will account for any additional treatment requests for SUI and/or OAB if initiated prior to the 1 year time point.

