5.4. Intervention - See Appendix A for the full BPTx Intervention Protocol

As stated above, for the intervention the team focused on evidence-based BPTx strategies. When evidence was lacking, the team made decisions based on the most logical and pragmatic rationale with a focus on developing a reproducible and standardized protocol.

For the purposes of this proposal “Behavioral training” (BPTx) will include:

1. Pelvic floor muscle training
2. Urge strategies defined in the field (included in intervention handout)
3. Stress strategies defined in the field (included in intervention handout)
4. Delayed voiding techniques (included in intervention handout)

The intervention will include 1 preoperative BPTx intervention visit and 5 post-operative intervention visits at 2, 4, 6, and 8 weeks and 6 months postoperative. Data from the ATLAS trial demonstrated that adherence with BPTx strategies decreased after 6 months, corresponding to a potential decrease in benefit.¹¹⁰ Therefore, a 6 month BPTx intervention session is part of the intervention in ESTEEM. Participants randomized to intervention will receive BPTx implemented by an experienced registered nurse, nurse practitioner or physical therapist. Patients will be monitored using an adherence questionnaire.

The intervention will be **standardized** through the following mechanisms:

- a. Certification of all interventionists through passing of e-learning modules and attendance and demonstration of hands-on skills at a 2-day, in-person interventionist training session
- b. There will be an interventionist checklist to ensure the same components have been performed across subjects
- c. There is a detailed protocol for the PFM exercise progression
- d. There is a detailed protocol for “special circumstances” for when the standard PFM exercise progression protocol cannot be followed (ie: weak muscle) that the interventionist will be required to follow
- e. Subject handouts will be developed for the 4 components (PFME, Urge strategies, stress strategies, and delayed voiding techniques) and the interventionists will be required to refer only to the handouts during the education component
- f. All intervention sessions will be audiotaped and a subset will be audited by behavioral therapy experts to ensure adherence to protocol. Any protocol deviations will be addressed as necessary.

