4.4 Masking and Data Lock

4.4.1 General Masking Procedures

Study surgeons and outcome assessors will be masked to treatment assignment. All outcome measures will be collected by masked outcome assessors. Study coordinators / clinical staff performing objective measurement of PFM strength will be masked (Aim 7). All patient-reported outcomes (PROs) will be administered prior to other clinical assessments or procedures.

It is not feasible to mask the patients or interventionists to the BPTx intervention due to the nature of the treatment being studied.

Study individual	Masking
Study participant	No
Interventionist	No
Outcome assessors (includes clinical staff performing PFM measurement)	Yes
Study surgeon	Yes

Efforts will be made by unmasked research assistant/staff members to remind the patient that the surgeon is masked to her treatment assignment. If she desires additional treatment, it is likely the surgeon would offer BPTx as additional treatment and she will be reminded that she can decline additional BPTx without revealing to her surgeon that she received the BPTx intervention. Such methods have been effective for past PFDN trials (e.g. OPTIMAL trial⁴²).

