16 ATTACHMENTS

16.1 Defining Treatment Failures and Retreatment Rates

Treatment failure is defined as initiation of any additional treatment for either SUI or UUI/OAB symptoms. These will be determined through an analysis of the Additional Therapy Form (CRF #31) and Concomitant Medications Form (CRF #28).

- a. Additional Therapy Form – Any subject with a reported reason for visit of 2, 3, 4, 5, 10, 11, 12, 13, 14, 15, or 17 will be considered to have treatment failure at the time of the reported treatment. Similarly, each subject will be considered to have had retreatment.

2. Reason for Visit	6 = Pain	10 = Botox	16 = Other, specify
1 = UTI	7 = Infection	11 = Posterior tibial nerve stimulation symptoms	17 = sling removal
2 = Behavior Therapy	8 = Decrease efficacy (worsening incontinence)	12 = sling revision	18 = UUI/OAB
3 = PF Therapy	9 = Retention of urine or incomplete bladder emptying	13 = sling placement	19 = SUI symptoms
4 = Anticholinergic medication		14 = sacral neuromodulation	
5 = Pelvic PT		15 = Continence pessary	

- b. Concomitant Medications – Any subject with medications or therapies that are known treatments of OAB, UUI, or SUI (Detrol, Ditropan, Vesicare, Hyoscyamine, Oxybutynin) or for whom UUI/OAB, SUI Therapy, or Voiding Dysfunction indicators are marked will be considered to have treatment failure at the start date of the medication if it is after randomization. Similarly, each subject will be considered to have had retreatment.

Medication Name	Start Date (DD/MMM/YYYY)	Stop Date (DD/MMM/YYYY)	PRN	UUI/OAB Therapy	SUI Therapy	Voiding dysfunction	Continuing at End of Study
	___/___/___	___/___/___					

In general, any adverse events that could be considered treatment failures will be requested to be removed and re-entered on the additional therapies form if applicable.

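### Does ignoring additional treatment undermine the 12-month pelvic floor muscle strength comparison, given that such treatment can itself be muscle training?

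*SAP*

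**What the plan says.** SAP 9.5.7 and Protocol 6.2.3.g analyse change from baseline in maximum contraction pressure with a general linear mixed model. It covers 8 weeks and 12 months, controls for the stratification factors, and includes a test of the group-by-time interaction. On additional treatment the instruction is: "Because additional treatment is not expected to impact this outcome, it will be ignored for the purpose of this analysis".

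Other places describe what that treatment can be and when it can start:

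- Protocol 3.4.1.c lists the options: "This may include (but is not limited to) behavioral and/or pelvic floor therapy, continence pessary, medical therapy".
- The same section sets the timing: "any additional treatment should be deferred until 3 months postoperatively".
- SAP 4.4.1 expects that "it is likely the surgeon would offer BPTx as additional treatment". Protocol 3.2 adds that "she will be reminded that she can decline additional BPTx".
- SAP 16.1 counts as failures "Any subject with a reported reason for visit of 2, 3, 4, 5, 10, 11, 12, 13, 14, 15, or 17". Codes 2, 3 and 5 are behavior therapy, pelvic floor therapy and pelvic physical therapy.
- SAP 9.5.7 says of muscle training that "incontinent women can improve their maximum contraction pressure up to 34-41 cm" H2O, against a starting value of about 25.

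**The concern.** The power statement for strength relies on training adding 10 to 15 cm H2O when it is the randomized intervention. Two paragraphs later, treatment that may consist of the same training is said to have no effect on strength. Both cannot be right.

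The timing gives the conflict some force. Additional treatment starts after month 3, so it falls between the two analysed measurements. If more controls than BPTx women take up training, the 12-month difference narrows relative to 8 weeks, and the interaction test may pick that up. A reader could take the narrowing for a BPTx effect that wears off. Real wearing-off is also possible: Protocol 5.4 cites earlier trial data in which "adherence with BPTx strategies decreased after 6 months, corresponding to a potential decrease in benefit". No planned sensitivity analysis examines additional treatment for strength. At stake are the size of the 12-month difference and the reading of the interaction test, both within one exploratory aim.

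**Working it through.** **1. The plan's own figures.** Inputs from SAP 9.5.7: 400 women (200 per arm), SD 13. Alpha is not stated for strength; 0.05 two-sided is assumed. The standard error of a difference in means is 13 × √(2/200) = 1.30. Power is Φ(3.66/1.30 − 1.96) = 0.80 and Φ(4.23/1.30 − 1.96) = 0.90, so both stated detectable differences reproduce. Power for a 10 cm difference exceeds 0.999.

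**2. Dilution at 12 months.** Let g be the gain from training, rC and rB the additional-treatment rates in control and BPTx, s the share that is muscle training, and h the further gain in women already trained. Then

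difference = g − rC·s·g + rB·s·h.

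The documents give g = 10 to 15 (35 or 40 against 25) and planning rates of 30% and 20%, a 3:2 ratio (SAP 6). They do not give s or h; s = 0.5 and h = 5 are assumed. SAP 13 calls failures relatively few but gives no count, so control rates of 5% and 10% are assumed at the same 3:2 ratio. With g = 10:

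| Control / BPTx rate | Calculation | Difference (cm H2O) | Shift |
|---|---|---|---|
| 5% / 3.3% | 10 − 0.25 + 0.083 | 9.83 | 0.17 |
| 10% / 6.7% | 10 − 0.50 + 0.17 | 9.67 | 0.33 |
| 30% / 20% (planning) | 10 − 1.5 + 0.5 | 9.0 | 1.0 |

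With g = 15, the 10% row gives 15 − 0.75 + 0.17 = 14.42, about 4% smaller. If already trained women gain nothing further (h = 0), the 10% row gives 9.5 for g = 10 and 14.25 for g = 15, each 5% smaller.

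**3. Interaction test, g = 10.** For a correlation ρ between the two measurements (assumed 0.5 or 0.7), the standard error is 13 × √(2(1 − ρ)) × √(2/200) = 1.30 or 1.01. If the BPTx gain is fully sustained, the two-sided 5% test rejects with probability Φ(−1.96 + shift/SE) + Φ(−1.96 − shift/SE):

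- shift 0.17: 5.2-5.3%
- shift 0.33: 5.8-6.3%
- shift 1.0: 12.0-16.8%

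The excess over 5% is not inflated type I error for the comparison the plan makes. When arms are compared regardless of later treatment, control training is part of the contrast, and a narrowing between the two times is real.

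**4. Women involved.** At a 10% control rate and s = 0.5, these are 200 × 0.10 × 0.5 = 10 controls and 200 × 0.067 × 0.5 ≈ 7 BPTx women.

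**5. What the plan already shows.** The model in SAP 9.5.7 yields mean change by arm at 8 weeks and at 12 months. Training among controls appears as a rising control mean; fading appears as a falling BPTx mean. Adherence in the BPTx arm is recorded at 6 and 12 months (SAP 4.6), and SAP 9.5.7 plans to assess its effect. Exploratory aim 5 compares the types of additional treatment by arm.

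**The case for a change.** The strongest reply is that a false premise in two governing documents should not stand merely because its effect is small, and that the plan already runs an additional-treatment sensitivity analysis for voiding frequency (SAP 9.5.1). Strength could be treated alike, using codes already collected. Aim 5 counts are not tied to the strength result, and means by arm are not a formal separation of fading from control training. At the limit (planning rates, every additional treatment being muscle training, no further gain under BPTx) the difference falls from 10 to 7.0 cm H2O and the interaction test rejects in 64-85% of trials.

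The wording conflict stands in full. The limit case does not carry the point. It needs the 30% and 20% rates, which SAP 6 supports largely with anticholinergic use, to consist wholly of muscle training, and SAP 13 says failures were relatively few. Even there, power for the 12-month contrast is about 0.998 or higher. A run that sets strength to missing after such treatment would assume missing at random in women selected by treatment failure, with only early values to inform it. It would miss training recorded under the free-text code or done without a visit. On about 17 women of 400 it would barely move the estimate. SAP 2 already permits it if the counts turn out to matter.

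**Conclusion.** No change is needed. The stated reason is wrong on the documents' own evidence, but the instruction it supports is right: strength is compared by randomized arm regardless of later treatment, consistent with SAP 5.1 and 9.1. An analyst following the plan as written gets a valid result. The expected effect on the 12-month difference is 2-3% (9.83 to 9.67 against 10 cm H2O), with interaction rejection of about 5-6%. At the planning rates it is 10%, with rejection of 12-17%. These figures rest on assumed values for the observed rate, the share that is muscle training, the further gain in trained women and the correlation between measurements. The conclusion that the comparison is valid does not depend on them. The primary and secondary outcomes, the 8-week contrast and the stated power are unaffected. The means by arm, the adherence data and the aim 5 treatment types give a reader enough to interpret any narrowing by 12 months.

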f. To determine MIDs and clinically meaningful MUI definitions that predict clinical outcomes.

We will explore potential MIDs for UDI total score and stress and irritative subscores for this MUI population. MIDs will be calculated using anchor- and distribution-based approaches. Potential anchors include global impression of change, incontinence episodes from the bladder diary, and request for additional treatment.

We will attempt to create threshold definitions, based on baseline measures of the UDI, IIQ, OAB-q, UDE, and baseline bladder diary parameters in isolation and in combination, that are predictive of clinical success at 1 year. Definitions of success will be based on a change from baseline in total UDI score, UDI-irritative score or UDI-stress score at least as large as the MID for this MUI population.

g. To compare pelvic floor muscle strength changes between women randomized to combined MUS+BPTx versus MUS alone, to estimate associations between pelvic floor muscle strength improvement and UI symptoms, and to identify predictors of unsuccessful pelvic floor muscle strengthening and urge suppression and their effects on urinary outcomes in women randomized to BPTx

As mentioned above, all women will undergo PFM strength measurements using the Peritron device by masked coordinators at baseline, postoperative at 2 weeks, 8 weeks (end of intervention), and 12 months (primary endpoint). The difference in the maximum pelvic floor muscle contraction pressure (maximum amplitude) will be compared between the BPTx and the control groups. A table of comparative

studies using the Peritron device to measure PFM strength changes with PFM therapy is provided in Table 12 below.

Based on the existing comparative studies using the Peritron, continent women have a maximum amplitude PFM contraction between 36-45 cm H₂O. Incontinent women have significantly lower maximum contractions, ranging from 15.5 to 26.5 cm H₂O, with most studies showing a maximum contraction of 25 cm H₂O. In these studies, incontinent women can improve their maximum contraction pressure up to 34-41 cm H₂O with PFM training, which is comparable to continent women. In addition, these studies report women experience significant improvement in UI symptoms, although there is limited information on the direct specific relationship between PFM strength changes and UI symptom changes.

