3.1.3 Exploratory Aims

Exploratory aims of this study include the following:

1. Assess whether combined MUS+BPTx is superior to MUS alone for improving the number of urgency and urge incontinence episodes on bladder diary at 1 year following MUS surgery.
2. Compare time-to-failure between MUS+BPTx versus MUS alone, where failure is defined as initiation of any additional treatment for lower urinary tract symptoms (SUI, UUI/OAB, or voiding dysfunction).
3. Develop models to identify predictors of change of MUI, OAB, and SUI outcomes measured using the UDI between baseline and 1 year post-treatment.
4. Compare quality of life outcomes, Patient Global Impression-Improvement (PGI-I), and Patient Global Impression-Severity (PGI-S) between groups
5. Describe rates of reoperation (sling revision) for worsening OAB symptoms after MUS and to compare the proportion of women in each group initiating additional treatment for SUI and/or OAB, and the types of additional treatment (BPTx, medications, other)
6. Determine MIDs and clinically meaningful definitions of MUI that predict clinical outcomes using cut-offs and combinations of standardized measures
7. Compare pelvic floor muscle strength changes between women randomized to combined MUS+BPTx versus MUS alone and to estimate associations between pelvic floor muscle strength improvement and UI symptoms. We will also explore predictors of unsuccessful pelvic floor muscle strengthening.
8. Determine the cost effectiveness of combined midurethral sling (MUS) and peri-operative behavioral/pelvic floor therapy (BPTx) compared to MUS alone for the treatment of MUI symptoms

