Change from Baseline Brink Score at 12 months	Continuous	The Brink Score will be calculated from the pelvic floor muscle assessment form. It is calculated by summing the Brink pressure, duration, and displacement metrics if the assessment could be performed (i.e. not unable to perform due to pain). The outcome will then be computed as the difference in Brink Score at 12 months (and 6 months) and the Brink Score at baseline. If data for the assessment time point are missing, the outcome variable will be coded as missing.
Change from Baseline Maximum Pelvic Floor Muscle Contraction Pressure (Maximum Amplitude) at 12 months	Continuous	The maximum amplitude from the Peritron device will be averaged across the valid squeeze measures (out of 3 possible). The outcome will then be computed as the difference in average maximum amplitude at 12 months (and 8 weeks) and the average maximum amplitude at baseline.

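### Exploratory Aim 7 asks about strength improvement, but the only clearly stated association analysis correlates strength and symptom levels at baseline and at 12 months

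*SAP*

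**What the plan says.** Aim 7 has an arm comparison, an association part and a predictor part. The association part is "to estimate associations between pelvic floor muscle strength improvement and UI symptoms" (SAP 3.1.3; Protocol 1.3 has the same wording). The rationale in Protocol 6.2.3.g, repeated in SAP 9.5.7, says of earlier studies that "there is limited information on the direct specific relationship between PFM strength changes and UI symptom changes".

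The analysis text in SAP 9.5.7, which matches Protocol 6.2.3.g, has three relevant elements:

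- Strength change is analysed by arm. The plan will "compare the mean change from baseline in PFM maximum contraction strength between the BPTx and control groups at 8 weeks and at 12 months" with a linear mixed model. Symptoms are not in that model.
- Strength and symptoms are joined in one sentence: "We will estimate the correlation between PFM strength and UI symptoms at baseline and at 12 months".
- Regression models will "explore potential predictors of unsuccessful pelvic floor muscle strengthening and urge suppression and their effects on urinary outcomes". The protocol's heading for item g lists this as an objective of its own: "to identify predictors of unsuccessful pelvic floor muscle strengthening and urge suppression and their effects on urinary outcomes in women randomized to BPTx".

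SAP 9.2 defines the change variables. Strength change is the "difference in average maximum amplitude at 12 months (and 8 weeks) and the average maximum amplitude at baseline". UDI change from baseline is defined at 3, 6 and 12 months. No sentence explicitly links the two.

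**The concern.** The aim is about improvement. A correlation at baseline precedes all treatment and holds no information on response. A correlation at 12 months mixes the strength a woman already had with what she gained. If the arms are pooled, it also mixes in any arm difference in either measure; the plan does not say whether they are pooled. The symptom side at 12 months largely reflects a sling that both arms receive.

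A report on whether strength gain goes with symptom improvement would therefore rest on a statistic that does not estimate it, or on a model chosen after the data are seen. That would be a loss, because masked staff measure strength objectively in all women at four time points, and Protocol 3.4.3.e gives the scarcity of evidence on strength and symptom improvement as the reason for doing so.

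**Working it through.** **1. The plan's own figures.** SAP 9.5.7 gives detectable arm differences of 3.66 (80% power) and 4.23 cm H2O (90% power), with SD 13 and 400 women. With 200 per arm and two-sided alpha 0.05 (assumed for this outcome), 13 × √(2/200) × (1.960 + 0.842) = 3.64, and with 1.282 in place of 0.842 it is 4.21. A noncentral t calculation gives 3.65 and 4.22. The figures reproduce, but they concern the arm comparison. No figure is given for the correlation analysis.

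**2. What the level correlations leave open.** Let X be strength and Y symptoms, standardised, with equal variances at both times. Let r0 and r12 be the level correlations at baseline and 12 months. Let c1 and c2 be the cross-time correlations (baseline strength with 12-month symptoms, and 12-month strength with baseline symptoms). Let ρX and ρY be the within-woman correlations over time. Then

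corr(ΔX, ΔY) = (r0 + r12 − c1 − c2) / (2√((1 − ρX)(1 − ρY))).

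The plan estimates r0 and r12 only. Take r0 = r12 = -0.30, ρX = ρY = 0.5 and c1 = c2 = c (all assumed). The formula becomes -0.60 − 2c, and the correlation of strength change with 12-month symptoms is -0.30 − c.

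| c | strength change with symptom change | strength change with 12-month symptoms |
|---|---|---|
| 0 | -0.60 | -0.30 |
| -0.15 | -0.30 | -0.15 |
| -0.30 | 0.00 | 0.00 |
| -0.45 | +0.30 | +0.15 |

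Every row is a valid correlation matrix, and a simulation of 200,000 draws agreed to within 0.01. The last row needs cross-time correlations stronger than same-time ones, which is less natural. Even without it, the two planned numbers fit anything from a marked association to none. The last column shows that this is also so if symptoms means the 12-month level and not its change.

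**3. The same in trial units.** From the documents: baseline strength 25 (SD 13), BPTx gain 10 (to 35), UDI baseline SD 49 (BE-DRI, Protocol 3.4.1), SD of UDI change 50.4 (SAP 6.1). Assumed: SD of gain 9, and correlation of baseline UDI with its change -0.6.

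- Variance of 12-month UDI: 49² + 50.4² − 2 × 0.6 × 49 × 50.4 = 1977.6, SD 44.5.
- Variance of 12-month strength pooled over arms, with gain unrelated to baseline: 13² + 9² + 10²/4 = 275, SD 16.6.

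*Gain matters.* Let gain and UDI change correlate at -0.30 within arm, with baseline levels unrelated. The covariance is -0.30 × 9 × 50.4 = -136.1. The planned correlations are 0.00 at baseline and -136.1 / (16.58 × 44.47) = -0.19 at 12 months.

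*Gain does not matter.* Let baseline levels correlate at -0.30, with baseline strength related to UDI change only through baseline UDI. The covariance is -0.30 × 13 × 49 + 0.18 × 13 × 50.4 = -73.2. The planned correlations are -0.30 at baseline and -73.2 / (16.58 × 44.47) = -0.10 at 12 months.

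**4. How firm the -0.19 is.** It depends on choices the documents do not settle.

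- If the arm's gain of 10 acts on UDI at the within-arm slope (-0.30 × 50.4/9 = -1.68 per cm H2O, so -16.8 points), it becomes -0.24.
- If control strength keeps SD 13 at both times, as SAP 9.5.7 assumes, baseline and gain must correlate at about -0.35. It is then -0.22, or -0.28 with the arm effect as well.
- If, with SD 13 kept and no arm effect, baseline strength also relates to UDI change through gain, the covariance is -136.1 + 68.0 = -68.0 and the value is -0.11.

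So one true correlation of -0.30 gives 12-month values from -0.11 to -0.28.

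**5. What a change analysis could deliver.** By Fisher's z, with 400 women the 95% half-width near zero is 0.10, and r of about 0.14 (80% power) or 0.16 (90% power) is detectable. With 200 in one arm these are 0.14, 0.20 and 0.23. If UDI after additional treatment is set to missing at the planned rates of 30% and 20%, then 140 + 160 = 300 women remain. The figures become 0.11, 0.16 and 0.19, and for the 160 in the BPTx arm 0.16, 0.22 and 0.25.

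**The case against.** The strongest objection is that improvement is not ignored. The regression sentence ends with effects on urinary outcomes, and one natural reading relates failure to gain strength, which is a change concept, to those outcomes. The BPTx arm is where training gain is expected. This stands in part: a reader might infer that the plan contains nothing on improvement, and that goes too far. But it is unclear whether the effects are those of the predictors or of the unsuccessful strengthening. No cutoff defines unsuccessful. The protocol lists this as an objective separate from the association with improvement. At best it would dichotomise gain at an unstated threshold, and Protocol 3.4.1 rejects dichotomising the primary outcome because information is lost.

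Second, Aim 7 speaks of symptoms, not symptom change; the change wording describes earlier studies. That is fair, so a change-on-change model is a choice and not the only reading. It does not rescue the level correlations, which do not identify the association of gain with 12-month symptoms either.

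Third, the aim is the seventh of eight exploratory ones, SAP 7.7 assigns the 0.05 level only to the primary and two secondary hypotheses, and SAP 2 allows further exploratory analyses without an update. All of this limits the weight of the point. It does not make it redundant: the statistic that is written down misses its own aim, and a model added later would not be prespecified.

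A reader might also infer that the trial will judge on this statistic whether strengthening explains any benefit of BPTx. Neither document plans a mediation analysis or a decision rule; SAP 9.5.7 only promises to estimate a correlation.

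**Conclusion.** The point holds as a mismatch between an exploratory aim and its stated statistic. Level correlations at two times do not determine the association with strength improvement, and the regression sentence does not clearly fill the gap.

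The size cannot be stated as a single bias. Under the assumed correlations, one pair of planned results (-0.30 and -0.30) fits change correlations from -0.60 to +0.30, and one true within-arm correlation of -0.30 gives 12-month values from -0.11 to -0.28. It is tempting to conclude that the planned correlation will understate a real association by a known amount. The documents give no correlations between strength and symptoms, and at the upper end of that range the understatement almost disappears.

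The primary and secondary comparisons, the sample size and the arm comparison of strength are unaffected.

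**What to change.** In SAP 9.5.7 and Protocol 6.2.3.g:

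- Add a prespecified exploratory regression of change in UDI total, stress and irritative scores from baseline to 12 months on change in Peritron maximum amplitude from baseline to 12 months. Fit a second version with change from baseline to 8 weeks as an earlier predictor. UDI is not collected at 8 weeks (SAP 4.6), so that gain can be paired only with later symptoms.
- Adjust for arm, baseline strength, baseline UDI, site and urge-IE group, and also report the model within the BPTx arm.
- State that UDI values after additional treatment are set to missing, as in the primary analysis, with a sensitivity analysis using all values. SAP 9.5.7 ignores additional treatment for strength, but SAP 9.3 expects it to affect UDI.
- Keep the two level correlations as descriptive results, and say whether arms are pooled.
- Define unsuccessful strengthening, and say what the regression sentence relates to urinary outcomes.

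The cost is wording in both documents and one more exploratory model on data already collected. The model is observational: strength gain is not randomised, so it cannot by itself show that gain causes the benefit.
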